5.4 DATA SAFETY MONITORING PLAN

5.4.1 SAFETY OVERSIGHT

Principal Investigator (PI) will be responsible for ensuring participants' safety on a daily basis. The Independent Safety Monitor will act in an advisory capacity to monitor participant safety, to evaluate the progress of the study, and to review procedures for maintaining the data confidentiality, collection quality, management, and analyses.

5.4.1.1 INDEPENDENT SAFETY MONITOR

[name] – Professor at Yale University School of Medicine

The Independent Safety Monitor will oversee the safety of the participants and the validity and integrity of the data. Responsibilities will include:

- Evaluating the research protocols and plans for safety and data monitoring
- Evaluating the progress of the study, including periodic assessments of data quality and timeliness, participant recruitment, accrual and retention, performance of the trial sites, and other factors that can affect study outcome
- Considering factors external to the study when relevant information becomes available, such as scientific or therapeutic developments that may have an impact on the safety of the participants or the ethics or practicality of the trial
- Reviewing study site performance, making recommendations and assisting in the resolution of problems reported by study team
- Ensuring the confidentiality of the trial data and the results of monitoring

5.4.1.2 INDEPENDENT SAFETY MONITOR MEETINGS

The PI will meet annually with the ISM by teleconference. At each meeting the ISM will review individual SAEs and cumulative AE reports. Following each meeting, the monitor will make recommendations on continuation, modification, or termination of the study.

5.5 COVID-19 REGULATIONS

Study staff will follow UW Human Subjects Division protocols regarding COVID-19 safety. Staff members will wear recommended face coverings in accordance with UW guidelines to prevent possible SARS-CoV-2 transmission, and will ask participants to do the same. When possible to do so while maintaining confidentiality, visits will be conducted in well-ventilated spaces, rooms with open windows, contained spaces outdoors, etc. As is expected at the time of writing, staff members will complete the COVID-19 Symptoms Self-Attestation for On-Site Personnel and Visitors on Workday prior to conducting in-person visits. As recommendations and protocols for COVID-19 safety are subject to change, we will adjust our procedures to match the most up-to-date recommendations and protocols available.

Kelley-Ross Pharmacy Program and HEP staff will operate under the COVID-19 safety protocols of their respective home agencies.

6 STATISTICAL ANALYSES

This study will provide estimates of what proportion of HCV-infected PWID successfully link to and utilize the community-pharmacy model.

The primary feasibility/acceptability outcome will be the proportion (and 95% confidence intervals) of participants who are evaluated for HCV treatment in the community-pharmacy program. Secondarily, we will evaluate HCV treatment outcomes (initiation, completion, and SVR12/cure), medication adherence, substance use, HIV risk

behaviors, and receipt of other medications (naloxone, PrEP, and medications for OUD). Finally, we will assess treatment satisfaction and willingness to refer an injecting partner to the community pharmacy for treatment.

Given our estimated sample size of 40 we can provide a range of estimates and 95% confidence intervals (CIs) for the following hypothetical scenarios: Using binomial “exact” calculation to estimate CIs, if we assume 0.5 of the sample (i.e., 20/40 participants) achieves the outcome, the estimated 95% CI is 0.34 to 0.66. If 10/40 achieves the outcome (0.25), the estimated 95% CI is 0.13-0.41; if 30/40 achieves the outcome (0.75) the estimated 95% CI is 0.59-0.87.

Name	Relation to you  Friend  Family member (specify): _____  Case manager  Other:
Best way(s) to contact them:  Cell phone  Landline phone  Text  Email  Facebook message  Other social media: _____	Cell phone#: _____ Landline#: _____ Email address: _____ Social media handle/link: _____

Alternate contact 2

Name	Relation to you  Friend  Family member (specify): _____  Case manager  Other:
Best way(s) to contact them:  Cell phone  Landline phone  Text  Email  Facebook message  Other social media: _____	Cell phone#: _____ Landline#: _____ Email address: _____ Social media handle/link: _____

8.2 IRB-APPROVED SCREENING SCRIPT

My name is _____, and I am part of a UW research team. I am talking with individuals to see if they qualify for a study we are doing, and if they are interested in participating. Participants in this study will receive HEP patient navigation services and will be linked to a community pharmacy program, where they may be offered several medications, including those that treat HCV. I am interested in asking you some questions to see if you may be eligible for this study. Would you like to be screened?

- Yes → *Continue with screening.*
- No → *Thank individual for their time, end screening.*

Before we start, I want to provide you with more information about this eligibility survey. You will not be compensated for the answers you provide for this eligibility survey. Participation in the study is not required; it is entirely your choice to participate and saying yes right now does not mean you have to be in the study. This survey will take just a few minutes. The answers you provide will be assigned a unique ID and stored in our password protected computer. If you are eligible to participate in the study, I can explain more about the study. Is this okay with you?

- Yes → *Continue with screening.*
- No → *Thank individual for their time, end screening.*

8.2.1 ELIGIBILITY SCRIPT

Eligible – *Thank you for your time. I'd like to briefly explain more about the study you are eligible for. Participants in this study will be linked to a community pharmacy program where they will be offered medications that (1) treat hepatitis C, (2) treat opioid use disorder, (3) prevent overdose, and (4) prevent HIV infection. You may get other medications that you need through the pharmacy program, too. We are interested in whether this new method of offering hepatitis C medications through a community pharmacy program that is convenient and accessible for people who inject drugs, who are living with hepatitis C, in Seattle. We will have two study visits over six months. Upon completing the first visit, you will receive a \$30 cash or gift card honorarium, and for the second you will receive a \$50 cash or gift card honorarium.*

We will also review your medical records related to receiving medications that treat hepatitis C, treat opioid use disorder, prevent overdose, and prevent HIV. We will complete a release of information together that gives the study staff access to this information. Your enrollment in the study is contingent upon completing this paperwork. If you are interested in learning more and participating, we can review the consent process and discuss more details of the study.

Are you interested in participating?

- Yes
- No → Why are you uninterested in participating? (Select all that apply)
 - Too busy
 - No interest in participating in research
 - Transportation difficulties
 - Other – Please specify: _____

Ineligible – *It looks like you are not eligible for this research study. We are looking for people with a different combination of characteristics. Thank you for your time today.*

8.3 ADVERSE EVENT FORM

HepPSI Phase II Adverse Event Report Form

Adverse event- Any unfavorable and unintended sign (including an abnormal laboratory finding), symptom or disease temporally associated with the use of a medical treatment or procedure, regardless of whether it is considered related to the medical treatment or procedure.

This form is to be completed by HepPSI Phase II Research staff upon notice of an adverse event and updated until event is resolved and all necessary parties are notified of the specific singular event.

Adverse Event Record ID:	_____
Date of Report:	Date report was written.
Name of staff completing report:	First and Last Name of Research Staff Person
Research Role of staff completing initial report	 Research Assistant  Research Coordinator  Co-Investigator  Primary Investigator
Date Research Staff became aware of event:	Date Staff became aware of event
How did Research Staff become aware of event:	 Electronic Medical Record  Informant: Who was the informant?  Other: How did you become privy to the event?
Date of Event:	When did the event occur?
Participant's Study ID:	_____
Description of Event:	Describe the event – what happened, how did it happen, how upset does the participant seem, etc.

1. Was the event serious?
 
 YES (please indicate reason)  NO
	 Death  Life-Threatening  Hospitalization  Persistent or significant disability/incapacity  Result in birth defect  Breach of Confidentiality  Other – Specify the other serious outcome		

2. Was the event related to study participation?
 
 YES (please indicate degree of relatedness)  NO
	 Possibly Related  Definitely Related	
Justification for degree of Relatedness Refer to DSMP to explain reasoning for selected degree of relatedness.
	

3. Was the event expected?
	 YES	 NO	

4. Which organ system(s) were affected?
	 Blood and Lymphatic System Disorders	 Cardiac Disorders	 Congenital, Familial and Genetic Disorders
	 Ear and Labyrinth Disorders	 Endocrine Disorders	 Eye Disorders
	 Gastrointestinal Disorders	 Hepatobiliary Disorders	 Immune System Disorders
	 Infections and Infestations	 Injury, Poisoning and Procedural Complications	 Investigations
	 Metabolism and Nutrition Disorders	 Musculoskeletal and Connective Tissue Disorders	 Neoplasms Benign, Malignant and Unspecified (Including Cysts and Polyps)
	 Nervous System Disorders	 Pregnancy, Puerperium and Perinatal Conditions	 Product Issues
	 Psychiatric Disorders	 Renal and Urinary Disorders	 Reproductive System and Breast Disorders
	 Respiratory, Thoracic and Mediastinal Disorders	 Skin and Subcutaneous Tissue Disorders	 Social Circumstances
	 Surgical and Medical Procedures	 Vascular Disorders	

What is the severity of the event?
 
 Mild  Moderate  Severe
	
Justification for degree of Severity
 
Refer to DSMP to explain reasoning for selected degree of severity
		

If the answer to Q1 and Q2 above are “YES” and Q3 is “NO”, then:
 
 - Research staff should notify and report to Site PI within 24 hours of becoming aware of the event - Research Team should then notify the NIDA PO within 24 hours of the event by email and then submit a written follow-up plan to the PO within 2 days of the event. - Research Team should also plan to report the event to their Site IRB 			

Action taken by research staff following notice of event:
	
Describe action taken
 
Describe any actions staff took once they became aware of the event.
		

Is a planned follow-up need?
 
 YES (please indicate follow-up plan)  NO
	
Description of Follow-up Plan:
 
What is the Follow-up plan to resolve any issues?
		

Date of Follow-up plan implemented
	
What date was the follow-up plan implemented?
		

To be completed by PI upon notice of an event
 
 
  
Has the Site PI been notified of the event?
 
 YES (Please provide dates of notification and reviewed)  NO (notify Site PI immediately)
 	 
Notified: Click here to enter a date. Reviewed: Click here to enter a date. (Completed by Site PI)
 	
 
		
Has the Site PI been notified of the event?
 
 YES (Please provide dates of notification and reviewed)  NO (notify Site PI immediately)
	
Notified: Click here to enter a date. Reviewed: Click here to enter a date. (Completed by Site PI)

Has the Site PI been notified of the event?
 
 YES (Please provide dates of notification and reviewed)  NO (notify Site PI immediately)
	
Notified: Click here to enter a date. Reviewed: Click here to enter a date. (Completed by Site PI)
		

Does the Site PI believe that the event put greater than minimal risk than was previously known or recognized?	 Yes	 No
If the event is determined to be a Serious Adverse Event that is an unanticipated problem, then the NIDA PO needs to be notified.		
NIDA PO Notified?  YES (please note dates of contact)  NO	Initial Email Date: Click here to enter a date. Follow-up plan Email: Click here to enter a date.	
Has the site IRB been notified of the event?	 Yes	 No
Date of Site IRB notified:	Click here to enter a date.	
Action Requested by IRB:  YES (please describe IRB action)  NO	IRB Requested Action Describe the requested IRB action.	
Date of IRB Action Request:	Click here to enter a date.	
Date of NIDA PO notified of IRB Action Request	Click here to enter a date.	
Outcome of Event:	 Unresolved – yet to be reviewed by PI  Ongoing – PI reviewed, waiting for responses from necessary parties  Unknown (lost to f/u)  Resolved – No more further action required (Resolved Date: Click here to enter a date.)  Death (Date: Click here to enter a date.)	
Will the participant continue study involvement?	 YES	 NO

Additional Notes

Actions to be taken by HepPSI Phase II Research Staff for Events

Unanticipated Problems

If the event is 1) **serious**, resulting in at least one of the 5 listed outcomes and/or causes greater risk of harm than was previously known or recognized (i.e. "Other"); 2) either possibly or definitely **related to the participant's study involvement**; and 3) **unexpected**, then research staff must do the following for this unanticipated problem:

- Report to Site PI, [name] within 24 hours of becoming aware of the event ([contact])
- Report to NIDA PO within 24 hours by email and submit a written follow-up within 2 days of the event [*NIDA PO – [name] ([contact])*]
- Report to IRB
 - o UW – ([link to UW HSD IRB Reporting Guidelines](#))
 - If the event is a breach (risk or loss) of confidentiality – report event to IRB within 24 hours.
 - If the event did not result in breach of confidentiality but still an unanticipated event UW Research Team must report to IRB within 10 business days of the event

Events that are not unanticipated problems

If the event is not considered to be an unanticipated problem, then the event is considered an AE/SAE and will need to be reviewed by research team at the following weekly meeting. In addition, research staff then must do the following:

- Report to Site IRB
 - o UW – Report recommendations made by the ISM at yearly meetings as Reportable New Information.
- Report all AE/SAEs to NIDA PO at annual continuing review/progress reports (i.e. RPPR and 6-month review)
- Report all AE/SAEs to ISM during annual Data Safety Monitoring Meeting

ISM Reviews and Reports

All individual SAEs and cumulative AEs are to be reviewed by the project's designated Independent Safety Monitor, [name], annually. Research staff will be notified a month prior to the meeting to begin preparing all reports for review. Following the annual ISM AE/SAE Review, reports and, if needed, plans of action to modify study design to improve participant safety will be submitted to the IRBs. Reports are to be shared with the NIDA PO within a month of being written.

UW – must send in Data Safety Monitoring reports and audit reports, regardless if changes are requested or not, within 10 days following the review

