5.3.3.2 RELATIONSHIP TO STUDY INTERVENTION

The site investigator assesses the potential event relationship to the study intervention and/or participation. A comprehensive scale in common use to categorize an event is:

- **Definitely Related:** The adverse event is clearly related to the investigational agent/procedure – i.e. an event that follows a reasonable temporal sequence from administration of the study intervention, follows a known or expected response pattern to the suspected intervention, that is confirmed by improvement on stopping and reappearance of the event on repeated exposure and that could not be reasonably explained by the known characteristics of the subject's clinical state.
- **Possibly Related:** An adverse event that follows a reasonable temporal sequence from administration of the study intervention follows a known or expected response pattern to the suspected intervention, but that could readily have been produced by a number of other factors.
- **Not Related:** The adverse event is clearly not related to the investigational agent/procedure. – i.e. another cause of the event is most plausible; and/or a clinically plausible temporal sequence is inconsistent with the onset of the event and the study intervention and/or a causal relationship is considered biologically implausible.

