5.3.4 ADVERSE EVENT (AND SAE) REPORTING

Adverse Events (AEs) and Serious Adverse Events (SAEs) have specific reporting procedures. AEs will be collected via REDCap. If REDCap is down, research staff should use the paper form **Adverse Event Reporting Form (See Appendix 8.3)**.

All AEs are collected on an Adverse Event Form that includes the date of the event, what occurred, actions taken by project staff, planned follow up (if any), whether the event appears to be related to the intervention, the seriousness of the event, and whether participant will continue in the study (see appendix). All AEs experienced by the participant during the time frame specified in the protocol (e.g., from the time of study drug administration through the end of the study intervention period) are to be reported.

Please note that the AE form contains a column to indicate whether the event is serious. Thus, SAEs are a subset of the reported AEs.

All SAEs, unless otherwise specified in the protocol and approved by the IRB or DSMP (as applicable), require expedited reporting by the Principal Investigator to the study's safety monitoring bodies. Serious adverse events will be reported to the site PI within 24 hours of research staff becoming aware of the event. SAEs that are unanticipated problems will be reported to the NIDA PO within 24 hours by email and a written follow up will be submitted within 2 days of the event.

Any IRB action response will be reported to NIDA PO within 3 days of the receipt of notice of the action.

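### The adverse event form gives the 24-hour notice to the site PI only to events marked serious, related and unexpected, whereas Protocol 5.3.4 requires it for every SAE

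*Protocol*

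**What the plan says.** Protocol 5.3.4 contains three separate duties.

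- **Staff to site PI:** "Serious adverse events will be reported to the site PI within 24 hours of research staff becoming aware of the event". No condition on relatedness or expectedness is attached.
- **To the funder's program officer:** "SAEs that are unanticipated problems will be reported to the NIDA PO within 24 hours by email". This duty is limited to unanticipated problems.
- **PI to the monitoring bodies:** "All SAEs, unless otherwise specified in the protocol and approved by the IRB or DSMP (as applicable), require expedited reporting by the Principal Investigator". This is the only one of the three with an exception clause.

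Protocol 8.3 then gives staff their working instructions.

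- The instruction box on the form opens with "If the answer to Q1 and Q2 above are “YES” and Q3 is “NO”, then". Questions 1 to 3 ask whether the event was serious, related and expected. The 24-hour report to the site PI is the first action under that condition.
- The action list after the form repeats the 24-hour PI report under its heading for unanticipated problems. Under the heading for all other events, which it labels AE/SAE, the event "will need to be reviewed by research team at the following weekly meeting". The remaining items there are reports to the IRB, the funder and the Independent Safety Monitor. None is to the site PI.
- The form's PI section asks whether the site PI has been notified, with the option "NO (notify Site PI immediately".

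On who judges relatedness, Protocol 5.3.3.2 says: "The site investigator assesses the potential event relationship to the study intervention and/or participation". The form in 8.3 is completed by research staff, whose role options run from research assistant to primary investigator.

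**The concern.** The form is what staff have in hand when an SAE occurs. Where it and the body text differ, the form is likely to be followed. A member of staff who marks an SAE unrelated or expected finds no 24-hour step to the PI in the instructions for that branch, although 5.3.4 requires one.

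The branch also depends on a judgement that 5.3.3.2 reserves for the site investigator. If a research assistant wrongly marks an SAE as unrelated, that answer removes the 24-hour step that would have put the event before the person meant to make the assessment.

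A second, smaller problem is the starting point of the external clocks. The PI clock starts when staff learn of the event; several funder and IRB clocks start at the event itself. What is at stake is timely oversight of participant safety and compliance with the protocol, not the study's estimates or confidence intervals.

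**Working it through.** The plan gives no figure to reproduce. The check compares texts, with a short count and a clock comparison.

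**1. Which SAEs carry the 24-hour PI notice.** Inputs: three relatedness levels (5.3.3.2: definitely, possibly, not related) and two expectedness levels (5.3.3.3). Classes of SAE = 3 × 2 = 6.

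| SAE class | 5.3.4 | Form and action list, 8.3 |
|---|---|---|
| Definitely related, unexpected | 24 hours | 24 hours |
| Possibly related, unexpected | 24 hours | 24 hours |
| Definitely related, expected | 24 hours | weekly meeting |
| Possibly related, expected | 24 hours | weekly meeting |
| Not related, unexpected | 24 hours | weekly meeting |
| Not related, expected | 24 hours | weekly meeting |

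Section 5.3.4 covers 6 of 6. The appendix covers 2 related levels × 1 expectedness level = 2 of 6, leaving 6 − 2 = 4. These are counts of classes, not shares of events; the documents do not say how often each class would occur.

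**2. Size of the gap in time.** Assume meetings exactly 7 days apart and no PI notice before the meeting. The wait is then 0 to about 7 days, against a limit of 1 day, so the excess is at most about 7 − 1 = 6 days. This is a worst-case reading; the appendix does not state a 7-day limit.

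**3. Does the exception clause reconcile the texts?** No. In 5.3.4 it qualifies expedited reporting by the PI to the safety monitoring bodies. The staff-to-PI sentence stands apart from it and is unqualified. The following sentence restricts only the funder report to unanticipated problems, so 5.3.4 itself treats the two duties differently.

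**4. Clocks.** Let L be the time from the event to staff awareness.

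| Report | Source | Runs from | Time left when staff learn of the event |
|---|---|---|---|
| Site PI, 24 hours | 5.3.4; 8.3 form and action list | awareness | 24 hours |
| Funder email, 24 hours | 8.3 form instruction box | event | 24 hours − L |
| Funder written follow-up, 2 days | 5.3.4; 8.3 form and action list | event | 2 days − L |
| IRB report, 10 business days (no confidentiality breach) | 8.3 action list | event | 10 business days − L |

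The form's wording for the email is "Research Team should then notify the NIDA PO within 24 hours of the event by email". If L exceeds 24 hours, that email is overdue before staff can act; if L exceeds 2 days, so is the written follow-up. The form also places the email after the PI report. The PI deadline falls at L + 24 hours after the event and the email deadline at 24 hours, so for any L above zero the email falls due before the step it is meant to follow.

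**The case against.** The strongest reply is that the appendix nowhere tells staff to withhold an SAE from the PI. The weekly meeting is a review step and does not forbid earlier notice. The form's question on PI notification applies to any event, its prompt asks for immediate notice, and it has fields for the dates the PI was notified and reviewed the event. This stands as mitigation. A reader might count the prompt as a third, conflicting rule; it is not, since immediate notice is compatible with 24 hours. It does not close the gap, however: it sits in the block marked for the PI to complete once notified, and it gives no hour limit.

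A reply on relatedness also stands in part. A co-investigator or the PI may complete the form, and the PI section includes a judgement of risk by the PI. A wrong call by non-investigators is therefore a possibility the form allows, not its rule.

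Three stronger readings are tempting and are not supported.

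- *The safety monitor would see incomplete data.* Protocol 5.4.1.2 and the 8.3 instructions give the monitor all individual SAEs and cumulative AEs every year, by either route. A delay of days to the PI removes nothing from that review.
- *Awareness may lag by about 60 days.* This rests only on the two-monthly research contact in 3.3.2. Navigators keep contact during treatment (3.3.3), follow up after appointments and ask about side effects, and check in monthly afterwards (8.4). The form also lists medical records and informants as sources. The documents give no bound on the lag.
- *Every 24-hour funder deadline is tied to the event.* Only the form's instruction box says so for the email. Section 5.3.4 and the action list give the email 24 hours with no stated starting point.

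**Conclusion.** The inconsistency is real and is in the current text. Section 5.3.4 gives all six SAE classes a 24-hour notice to the site PI; the form's instruction box and action list state it for two and send the other four to the next weekly meeting with no PI report listed. The form's general prompt reduces the practical risk without reconciling the texts. The possible delay of up to about 7 days assumes meetings 7 days apart and that nobody acts on the prompt; no actual delay is alleged.

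The clock problem also holds, for the 24-hour funder email on the form, the 2-day written follow-up and the 10-business-day IRB report. How often these would lapse depends on a reporting lag that the documents do not give.

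The primary proportion and its confidence interval are unaffected. The change should be made because staff who follow the form exactly can breach the protocol.

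**What to change.** Reconcile the form and action list in 8.3 with 5.3.4.

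1. Make the 24-hour notice to the site PI depend on Question 1 (serious) alone, both in the form's instruction box and in the action list, and print it outside the block the PI completes.
2. Have the site investigator then complete relatedness and expectedness, in line with 5.3.3.2, and use those answers to decide on unanticipated-problem reporting.
3. State in the list for other events that the weekly review does not replace the 24-hour notice for an SAE.
4. Count the funder email, the 2-day written follow-up and the 10-business-day IRB report from the date staff became aware of the event, which the form already records, and make the same change to the follow-up sentence in 5.3.4. Confirm the new starting point with the funder and the IRB.

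The cost is a wording change to one form, its instruction page and one sentence of 5.3.4, plus a few extra same-day messages to the PI in a study of 40 participants.
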